A total of 48 randomized participants are planned for the R21 phase. This sample size is based on Aim 1, which is to determine effects of VAR versus PLA on smoking urges and negative affect during abstinence, reinforcing effects of a smoking lapse, cognitive function and time to relapse in SS. A repeated-measures design with 48 total participants provides 80% power to detect main and interaction effects on the primary targets (smoking urges and negative affect during abstinence) and secondary targets (reinforcing effects of a smoking lapse) of at least $d = .40$ in size, assuming a moderate within-subject autocorrelation. While this effect size is somewhat smaller than those detected by West et al. (2008) for effects of abstinence on urges and negative affect during abstinence and smoking satisfaction and reward from relapse (d 's = .32-.44), abstinence was not controlled or biochemically verified after target quit date in that study, and, as the authors noted, it is possible that the effects that they observed were due only to those who were completely abstinent. With our rigorous control of abstinence, which includes twice-daily CO testing and a stringent abstinence criterion, we believe that we will detect smaller effects. We are not determining sample size based on Aim 2 (which is to examine the extent to which the effects of VAR on time to relapse are mediated through its effects on the target mechanisms), but we should be able to

detect medium-sized group effects on latency to second lapse, and estimate the size of mediation relationships that would be detectable as significant. We anticipate 20% attrition between enrollment and randomization. Therefore, we anticipate needing to enroll up to 60 participants (30 per group) to include 48 in the intent-to-treat sample.

R33 phase:

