cognitive measure scores (with baseline scores covaried), CPT demand indices and within-session changes (post- minus pre-smoking) in CO level and positive and negative mood scale scores. Significant interactions will be followed by simple effects tests. Those who opt not to smoke in Session 8 will not be included in the Group x Abstinence analyses of CEQ, or pre-to-post smoking changes in CO or mood, but will be included in all other analyses (only one SS opted not to smoke in Session 8 in our previous study, Tidey et al., 2014). Latency to relapse will be defined as hours between the start of Session 8 and time of relapse, collected in person at Friday's session and by videoed CO sample in the follow-up week. We will follow up for one week after Friday's session, which is 8 days after Session 8. Thus, the maximum latency until second lapse will be 192 h, at which point data will be censored. Lapse latencies will be compared in VAR vs. PLA using a t-test. We will examine whether gender and FTND score (≤ 5 vs. ≥ 6) moderate the effects of VAR by adding these factors (separately) to each model.

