Following intent-to-treat principles, all randomized participants will be included in analyses. Baseline characteristics of the groups will be compared using ANOVAs for continuous variables and chi-square tests for categorical variables. CO levels from participants' videos will be averaged to provide a single CO measure for each week. Effects of the treatment groups on dependent measures (CO, total and consecutive abstinent CO samples, cigarettes per day, cotinine, QSU, MNWS, mood, CEQ, Stage of Change, Contemplation Ladder, cognitive scores (baseline co-varied), BPRS, Calgary Scale, AIMS, Simpson-Angus and BARS scores), will be analyzed with generalized linear mixed models (GLMMs) with Group (VAR + CM, VAR + NR, PLA + NR) as the between-subjects factor and Session as the within-subjects factor. We will examine main effects and the Group x Session interaction. This approach controls for correlations from repeated measurements and for person-level covariates. Baseline data will be imputed for missing. Differences will be considered significant when $p \leq .05$ and effect sizes will be calculated (Cohen, 1988). We will examine whether gender and FTND score (≤ 5 vs. ≥ 6) moderate treatment effects by adding these factors (separately) to each model. To examine whether reductions in smoking are mediated by changes in proposed targets, once the Group x Session GLMMs have been conducted, we will add concurrent QSU, MNWS and CEQ Reward and Satisfaction scores as covariates in these models to see the extent to which

smoking outcomes are attenuated by the mediators. We will use the same procedure to explore whether cognitive performance mediates smoking outcomes.

Feasibility outcomes include: median number of sessions attended, percentage of video samples submitted and percentage of those who indicate that they would be willing to participate in a longer CM trial. Responses to open-ended questions on the debriefing questionnaire will be described. Number and type of serious adverse events are expected to be rare so will be reported descriptively. Adverse event ratings will be analyzed individually using one maximum value over the 5 weeks for each person for each expected effect, including the baseline value of each item.

Quality Assurance

Procedures in place to ensure the validity and integrity of the data

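### FTND moderation is tested with a ≤5 v ≥6 split in both phases; if moderation is roughly linear, keeping the graded score would use more of the information

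*Combined protocol and SAP*

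**What the plan says.** A sentence opening "We will examine whether gender and FTND score" stands in both phases of the Data Analysis Plan. In the R21 part of the Data Analysis Plan, the moderator analysis asks whether "gender and FTND score (≤ 5 vs. ≥ 6) moderate the effects of VAR by adding these factors (separately) to each model". The R33 part uses the same cut: "gender and FTND score (≤ 5 vs. ≥ 6) moderate treatment effects by adding these factors (separately) to each model". Neither place explains the cut, offers an analysis of the undivided score, or states which model term is the test of moderation.

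FTND is listed among the other smoking measures under Primary and Secondary Outcome Measures, so the full score will be in the data set. The Brief Description of Protocol says that the urn randomization stratifies on gender and dependence, but gives no cut-point for dependence.

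On size, Power Calculation and Sample Size states: "A total of 48 randomized participants are planned for the R21 phase". It adds: "This sample size is based on Aim 1". R33 also randomizes 48, across three groups, and is expressly not powered for group differences. No power is stated for moderation in either phase.

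**The concern.** A two-level FTND treats scores of 5 and 6 as different and all scores of 6 or more as the same. If the varenicline effect changes gradually with dependence, that throws away information that has already been collected.

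The test has little to spare. In R21, 48 people over two arms and two FTND levels leave at best 48/4 = 12 per cell. In R33, three arms leave at best 48/6 = 8. What is at stake is the power and precision of a pre-specified moderator analysis. The main comparisons are not at stake.

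**Working it through.** **The plan's own figures.** Enrolment reproduces: 48/(1 − 0.20) = 60, as in "enroll up to 60 participants (30 per group) to include 48 in the intent-to-treat sample". The 80% power for d = 0.40 cannot be reproduced uniquely, because the within-subject autocorrelation is called moderate without a number. For the Group main effect averaged over Sessions 2-8 with AR(1) correlation, power is 81% at 0.3, 73% at 0.4 and 65% at 0.5. None of these figures concerns moderation.

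**Inputs for the check.** From the documents: N = 48, two equal arms, cut at 5/6, significance level 0.05. Assumed: a two-sided test, an FTND scale of 0-10, the FTND mean and SD, and a linear moderator effect.

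**Information kept by the split.** Under linear moderation, the efficiency of the split relative to the score is the squared correlation between FTND and the indicator FTND ≥ 6. For a normal score with share p on one side of cut c (in SD units), this is φ(c)²/[p(1 − p)].

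- Cut at the median: 2/π = 0.637, a loss of 36%. Equivalent sample: 48 × 0.637 = 30.6, about 31 people.
- 40%, 30% or 20% of people on the smaller side: losses of 38%, 42% and 51%.
- Rounded 0-10 score, mean 5.8, SD 2: loss of 34%.
- Rounded 0-10 score, means 4 to 7 and SDs 1.5 to 2.5: losses from 32% to 54%.
- Flat 0-10 distribution: loss of 25%.

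**What this does to power.** A moderation effect with 80% power on the score has, after a median split, power Φ(√0.637 × (1.960 + 0.842) − 1.960) = Φ(0.28), or about 61%. Recovering 80% would take 48/0.637, about 76 people.

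**Simulation.** One outcome per person, two arms, N = 48, FTND rounded and bounded to 0-10 with mean 5.8 and SD 2 (assumed), interaction t-test:

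| True moderation | Continuous FTND | ≤5 v ≥6 split |
|---|---|---|
| Linear, 0.2 SD per FTND SD | 10% | 8% |
| Linear, 0.4 | 25% | 18% |
| Linear, 0.6 | 48% | 34% |
| Linear, 0.8 | 71% | 52% |
| Step of 1.2 SD at 5/6 | 35% | 52% |

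Repeat runs differ by a point or two. As a cross-check at 0.6, the normal approximation has SE = 2/√48 = 0.289, so 0.6/0.289 = 2.08. Power is Φ(2.08 − 1.96) = 55% for the score and Φ(0.798 × 2.08 − 1.96) = 38% for the split. These are a little higher than the simulated values, with a gap of similar size.

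**How small the test is in any case.** With 12 per cell, the SE of the difference between subgroup treatment effects is √(4/12) = 0.577 SD, so 80% power needs (1.960 + 0.842) × 0.577 = 1.62 SD on a single measure. With the score, 80% power needs (1.960 + 0.842) × 0.289 = 0.81 SD per FTND SD.

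**The case against.** There is a fair case for leaving the plan as it is.

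- **The loss is conditional.** It needs roughly linear moderation, and its size depends on an FTND distribution that the documents do not give. With a true threshold at 5/6 the advantage reverses. This stands, and it is why the loss is given as a range.
- **The gap is wide only for large effects.** The plan is built around d = 0.40. With an average effect of 0.40, a slope of 0.6 implies effects of −0.2 and +1.0 at 1 SD below and above the FTND mean, a change of sign. At slopes of 0.2 to 0.4 the gap is 2 to 7 percentage points, and neither coding is informative. This stands.
- **The simulation is not the planned analysis.** R21 adds the moderator to GEE models, mixed ANOVAs and a t-test, and R33 to three-arm mixed models. A reader might infer a known loss of power in R33. No R33 power figure was computed, so none is claimed.
- **Little depends on it.** Moderation is in no stated aim. A reader might take the claim that the design "provides 80% power to detect main and interaction effects on the primary targets" to cover the moderator interaction. That sentence describes a repeated-measures design for the Aim 1 targets and mentions no moderator, so no power commitment is broken.
- **The cut may mirror the randomization.** Gender and FTND match the two urn factors, and a fixed cut is not chosen from the data. But the urn cut is not stated. Even if it is 5/6, adjusting for a stratum needs only a main effect and does not require the interaction to be tested on the split.

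**Conclusion.** The point holds as a low-cost efficiency improvement. Both phases dichotomize a score that will be available in full, and give no reason. If moderation is roughly linear, the split loses about a third of the information on the interaction when scores centre near 5/6, and about 25-54% over the assumed distributions examined. A reader might go further and take a one-third loss as established. The documents do not support that, because they give neither the FTND distribution nor the shape of the moderator effect.

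A reader might also infer that a continuous score would make the moderator test adequate. It would not: the analysis is secondary and unpowered under either coding. The primary comparisons, the basis of the sample size and the go/no-go rule do not depend on it.

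**What to change.** In the R21 and R33 parts of the Data Analysis Plan, test Group x FTND with FTND as a continuous, centred score, and name that interaction as the term tested. Keep ≤5 v ≥6 as a descriptive or sensitivity analysis, which also guards against a threshold effect. State the dependence cut used in the urn. If it is 5/6, include that stratum as a main-effect covariate.

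The cost is a phrase or two in each place, with no change to data collection, conduct or sample size. The downside is that the main moderator test then assumes a roughly linear trend and is less sensitive to a true threshold at 5/6.

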DATA SAFETY MONITORING PLAN

NIH Grant number: R21 DA041114-01A1

Targeted Pharmacological and Behavioral Treatments for
Smoking in Schizophrenia

Principal Investigator: [name]., Brown University

Medical Monitor: [name]., Ph.D., Brown University

Version Date: May 19, 2017

Summary of the Protocol

Brief Description of Protocol

The prevalence of cigarette smoking among people with schizophrenia in the United States is two- to three-times that of the general population. Smokers with schizophrenia (SS) have very low rates of smoking cessation, resulting in a disproportionate burden of tobacco-related morbidity and mortality. The overall objective of this project is to develop a novel, theory-driven intervention for smoking cessation for SS. Varenicline (VAR) reduces relapse among SS who attain abstinence, but is less effective at inducing abstinence. Contingency management (CM) interventions are highly effective at inducing abstinence in SS, but relapse rates are high once the incentives are discontinued. The combination of VAR + CM may be optimal for both inducing abstinence and reducing relapse in SS, especially if VAR reduces target mechanisms that are posited to underlie early relapse in SS: smoking urges and negative affect during abstinence (primary targets), smoking reinforcement (reward and satisfaction) during a smoking lapse (secondary targets) and cognitive dysfunction during abstinence (exploratory target). In the R21 phase of this research, we will use a laboratory model to compare the effects of VAR and placebo (PLA) on time to relapse and on these primary, secondary and exploratory target mechanisms.

Aims of the R21 Phase

Aim 1: To examine the effects of VAR versus placebo (PLA) on smoking urges and negative affect during abstinence, reinforcing effects of a smoking lapse, cognitive function and time to relapse in SS.

Aim 2: To examine the extent to which the effects of VAR on time to relapse are mediated through its effects on the target mechanisms.

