In Session 1 (pre-medication baseline), we will collect baseline measures of smoking urge, withdrawal symptoms, mood, cognitive performance, a behavioral economics-based measure of cigarette demand and effects of smoking a cigarette on cigarette reward, satisfaction and mood. Next, participants will be randomized to VAR (1 mg twice daily for 3 weeks) or PLA, using urn randomization to stratify on gender and dependence. Participants will complete a week of medication use using the standard dose run-up (0.5 mg once daily on days 1-3, 0.5 mg twice daily on days 4-7, then 1 mg twice daily until the end of the medication period). In Session 2, which occurs after one week on medication, participants will complete the same laboratory assessments as in Session 1. Next, participants will undergo a 3-day abstinence period. They will come to the laboratory twice per day and will receive escalating cash incentives for breath carbon monoxide (CO)-verified abstinence. At each visit, cigarette craving and withdrawal symptoms will be measured. At Session 8 (Thursday morning), participants who have been continuously abstinent will complete the same procedure as in Sessions 1. For ethical reasons, participants who complete the study through Thursday and who wish to remain abstinent may opt out of smoking during this session and will still receive full compensation for participation, as long as they attend this lab session and complete the other session measures.

Participants will be asked to return to the laboratory on Friday morning. Breath CO will be measured and time of first lapse (single cigarette) and relapse (return to regular smoking) will be collected among those who have lapsed and relapsed. Those still abstinent ($CO \leq 4$ ppm) since Session 8 will receive a small cash incentive. Next, participants will be shown how to use breath CO monitors with smart phones to record

and text us videos of themselves providing CO samples twice per day for the following week to determine time to lapse and relapse. Participants will receive \$5 for each submitted sample (not contingent on CO level), paid when the smart phone and CO monitor are returned at the end of the week.

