All data will be collected for research purposes only. All forms will be marked with only subject ID, session number and date. All records will be stored in locked files (physical or on computer) in locked rooms accessible only to research staff. Data gathered from people who attend the screening but do not meet inclusion criteria or decide not to participate will be stripped of personal identifiers or links and only the reason for study exclusion will be kept.

Personal information (participant name, address, telephone number, email address, locator contact information) must be collected so that the research assistant can contact people to schedule assessments, call with session reminders and arrange transportation to sessions. These data will be stored in a locked file that does not contain ID code numbers. All other data will be stored in files locked in a separate location with only code numbers identifying subjects and no personal identifiers. A cross-index of code numbers and participant names will be kept in a separate, password-protected computer file that is available only to research staff, PI, and mandated agencies during audits (e.g., study sponsor and Brown University IRB).

Saliva specimens for cotinine analysis will be marked with a study ID number, stored in the locked laboratory suite, and sent to a commercial laboratory for analysis. We will track samples sent and analysis results received using a form stored on a password-protected computer.

Data Analysis Plan

R21 phase

Variables will be examined for distributional assumptions associated with analyses to be used and transformed if necessary. Groups will be compared on demographic and other individual difference measures using t-tests for continuous measures and chi-square tests for categorical measures. Analyses of the effects of Group (VAR, PLA) and Time (Sessions 2-8) on QSU and MNWS-negative affect scores will be conducted using generalized estimating equation (GEE) models (Zeger et al., 1988), which allow for varying numbers of observations per participant (to minimize bias due to attrition) while controlling for autocorrelation (AR1 structure). GEE will also be used to analyze the effects of Group and Time (Screening, Sessions 2 and 8) on BPRS and other psychiatric symptom scores. Mixed 2 x 2 Analysis of Variance tests (ANOVAs) will be used to examine effects of Group and Abstinence (Sessions 1 and 8) on CEQ scale scores,

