Mediation of the relationship between group and lapse latency will be examined using an SPSS macro (Preacher & Hayes, 2004). Hypothesized mediators will include baseline Calgary scale, cognitive performance and Contemplation Ladder scores, Session 8 QSU and MNWS scores, Session 8 CPT and CEQ Reward and Satisfaction scores, and Session 8 cognitive performance scores. Simple mediator models will be used to investigate the direct effect of medication on relapse latency (c path) with no mediator in the equation, as well as the medication \rightarrow mediator path (a), the mediator \rightarrow latency path (b), and the effect of medication on latency with the mediator in the equation (c' path). The indirect effect of medication on latency via each mediator ($c - c'$) is equal to the product of the coefficients of the "a" and "b" paths (i.e., "ab"). If ab is not normally distributed, 10,000 bootstrap resamples will be used to obtain lower and upper 95% confidence intervals (CI) for each indirect effect (Preacher & Hayes, 2008). All variables will be standardized first so that path coefficients can be directly compared across variables with different metrics. In addition, step-wise regression will be used to examine whether screening BPRS scores (entered in Step 1) and Session 8 BPRS scores (Step 2) predict latency to relapse. The SPSS mainframe statistical package (SPSS, Inc., Chicago, IL) will be used for GEE, mediation and regression analyses. All other analyses will be conducted using SPSS Statistics Version 20 for Windows (IBM, Armonk, NY). Differences will be considered significant when $p \leq .05$.

R33 phase

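### Baseline Calgary, cognitive and Contemplation Ladder scores are listed as mediators in Aim 2, but scores measured before randomisation cannot carry an effect of varenicline

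*Combined protocol and SAP*

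**What the plan says.** Aim 2 (Aims of the R21 Phase) asks how far the "effects of VAR on time to relapse are mediated through its effects on the target mechanisms".

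The mediation paragraph of the Data Analysis Plan, R21 phase, opens its list of candidates with: "Hypothesized mediators will include baseline Calgary scale, cognitive performance and Contemplation Ladder scores". The list continues with Session 8 scores: QSU, MNWS, CPT, CEQ Reward and Satisfaction, and cognitive performance. Session 8 cognition is a separate entry, so *baseline* governs the earlier cognitive entry. Each mediator gets the same simple model: an a path from medication to mediator, a b path from mediator to latency, and an indirect effect ab.

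On timing:

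- The Brief Description of Protocol collects cognitive performance in Session 1, before medication, and continues: "Next, participants will be randomized to VAR".
- The Data Analysis Plan sets the time points for psychiatric symptoms as "Group and Time (Screening, Sessions 2 and 8) on BPRS and other psychiatric symptom scores". The Calgary scale is listed as a psychiatric symptom measure under Primary and Secondary Outcome Measures, so its first value is at Screening.
- No R21 session is named for the Contemplation Ladder. Its timing rests on the word *baseline* in the mediator list.

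On the outcome: "Latency to relapse will be defined as hours between the start of Session 8 and time of relapse". On who completes that session: "participants who have been continuously abstinent will complete the same procedure as in Sessions 1".

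**The concern.** A mediator must lie between treatment and outcome. A score fixed before allocation cannot be changed by the drug, so asking how much of the drug effect passes through it has a known answer: none. Aim 2 asks about varenicline's effects on the target mechanisms, and a baseline score cannot answer that.

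The risk is one of interpretation. The output for these scores will look just like the output for real mediators, and an interval that happens to exclude zero would be a false positive presented as mechanism. The number of such tests is also not fixed. The outcome list names five cognitive tasks, so with one score per task there would already be 5 + 1 + 1 = 7 baseline indirect effects.

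**Working it through.** The plan gives no figure for the mediation analysis, so there is none to reproduce. The check is a short derivation, followed by a simulation of how the planned test behaves.

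**1. True value.** Let M be a score measured before randomisation. Then

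a = E[M | VAR] − E[M | PLA] = 0, so ab = 0 × b = 0, and c − c′ = 0, for any b.

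**2. Chance imbalance.** The Power Calculation section gives 48 randomised participants; I take 24 per arm. The standard error of a standardised baseline difference is √(2/24) = 0.289. The chance of an imbalance above 0.2 SD on any one score is 2 × P(Z > 0.2/0.289) = 49%. Above 0.4 SD it is 17%.

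**3. Spread of the estimate.** The plan standardises all variables. With a = 0, Var(ab) is approximately Var(a) × (b² + Var(b)), where Var(a) ≈ 1/47 and Var(b) ≈ (1 − b²)/45. For example:

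- b = 0: √[(1/47)(1/45)] = 0.022
- b = 0.7: √[(1/47)(0.49 + 0.51/45)] = 0.103

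**4. Behaviour of the test, all 48 analysed.** The simulation used a baseline score independent of arm, latency = b × score + noise with unit variance, and a percentile bootstrap with 1,000 resamples (the plan uses 10,000). There were 4,000 simulated trials per row. The values of b are assumptions.

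| Assumed b | SD of ab | 95% interval excludes zero |
|---|---|---|
| 0 | 0.022 | 0.1% |
| 0.1 | 0.026 | 0.6% |
| 0.3 | 0.048 | 2.4% |
| 0.5 | 0.076 | 6.2% |
| 0.7 | 0.103 | 6.3% |

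Mean ab is 0, and the Monte Carlo standard error of the rates is at most 0.4 percentage points. The SDs agree with step 3. A separate simulation with an added direct drug effect of 0.4 SD and 2,000 trials gave 0.1%, 3.4%, 5.0% and 6.1% for b = 0, 0.3, 0.5 and 0.7. Its SDs were about twice as large (0.20 at b = 0.7) because group was coded 0/1: 0.289 × 0.7 = 0.202, against (1/√47) × 0.7 = 0.102 with group standardised.

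**5. If only Session 8 completers are analysed.** The plan does not say who enters the mediation models. Latency starts at Session 8, and only continuously abstinent participants complete that session's procedure. If varenicline changes who gets that far, baseline scores can differ by arm among those who remain. The documents give no completion rates by arm, so the figures below are illustrative. The first two rows leave 24 × 0.8 + 24 × 0.5 ≈ 31 people. The slope is the assumed log-odds of completion per SD of the baseline score. The ranges cover b = 0.3 to 0.7, with 600 resamples and 2,000 simulated trials.

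| Completion, VAR / PLA | Slope | Mean ab | Interval excludes zero |
|---|---|---|---|
| 80% / 50% | 1 | −0.037 to −0.082 | 3.8% to 12.4% |
| 80% / 50% | 2 | −0.049 to −0.127 | 5.6% to 22.2% |
| 80% / 50% | 0 | 0 | 2.3% to 6.8% |
| 65% / 65% | 1 | 0 | 2.0% to 5.2% |

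Of these four scenarios, the indirect effect is biased away from zero only in the two where completion differs by arm and also depends on the score. That is selection, not mediation.

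**The case against.** The strongest reply is that little harm follows. The sample size statement says "We are not determining sample size based on Aim 2", the go/no-go rule rests on reduction in the targets, and with all 48 analysed the error rate per test is near or below 5%. The Session 8 scores on the same list still address the target mechanisms. All of this stands and limits the weight of the point.

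Second, the same model also yields b, whether the score predicts latency, and c′, the drug effect adjusted for the score. Both can be interpreted. That also stands: only the a path and ab are uninformative.

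Third, the selection figures rest on assumed completion rates and slopes. Selection would also affect the latency comparison and every Session 8 mediator, so deleting baseline entries does not cure it. This is fair, and the main conclusion does not depend on those figures.

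Fourth, the plan bootstraps only if ab is not normally distributed and does not name the alternative. If that were a normal-theory (Sobel) interval, which is an assumption, the exclusion rates with all 48 analysed would be 0.4%, 2.5% and 4.4% at b = 0.3, 0.5 and 0.7. Lower rates do not make the test meaningful.

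The authors may have meant predictors or moderators. The text says mediators, assigns a and ab paths to them, and elsewhere names only gender and FTND as moderators. If another role was intended, the wording still needs correcting.

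**Conclusion.** The concern holds. As written, the plan tests mediation through scores that the drug cannot affect, so their true indirect effects are zero by design among all randomised participants. The time order is explicit for cognition, follows from the Screening assessment for the Calgary scale, and is inferred from the word *baseline* for the Contemplation Ladder.

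In size this is a modest error confined to Aim 2. Per test, false positives run from 0.1% to 6.3% when everyone is analysed, under assumed b of 0 to 0.7, normal data and no censoring at 192 h. Higher rates need arm-dependent selection that the documents neither show nor exclude. Aim 1, the 48 participants and the go/no-go rule are unaffected. It should still be corrected, because Aim 2 is one of only two R21 aims and any positive result for these scores would be misleading.

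**What to change.** Remove the baseline Calgary, cognitive performance and Contemplation Ladder scores from the mediator list. Keep the Session 8 scores: QSU, MNWS, CPT, CEQ Reward and Satisfaction, and cognitive performance.

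If the baseline scores are of interest, give them a role that suits their timing. They can be predictors of latency, as the plan already does for the BPRS, where it will "examine whether screening BPRS scores (entered in Step 1) and Session 8 BPRS scores (Step 2) predict latency to relapse". They can also be moderators labelled exploratory, or covariates, as baseline cognition already is in the ANOVAs.

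Two related clarifications would help but are separate from this correction: state whether the mediation models include all randomised participants or only those who reach Session 8 abstinent, and report the bootstrap interval for every indirect effect.

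The cost is wording in the analysis plan. Sample size, visits, data collected and the go/no-go rule do not change.

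### The R21 mediation models omit the Session 1 value of each Session 8 mediator, so the mediator-to-latency path can be confounded by pre-drug level and the indirect effect biased

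*Combined protocol and SAP*

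**What the plan says.** Aim 2 of the R21 phase is "To examine the extent to which the effects of VAR on time to relapse are mediated through its effects on the target mechanisms". The Data Analysis Plan, R21 phase, sets out how: "Simple mediator models will be used to investigate the direct effect of medication on relapse latency", with the usual a, b, c and c' paths for each mediator. The c' equation, which also supplies b, is "the effect of medication on latency with the mediator in the equation". No covariate is named.

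The mediators measured on drug are "Session 8 QSU and MNWS scores, Session 8 CPT and CEQ Reward and Satisfaction scores, and Session 8 cognitive performance scores". These are levels, not changes from Session 1.

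The pre-drug counterparts exist. The Brief Description of Protocol states: "In Session 1 (pre-medication baseline), we will collect baseline measures of smoking urge, withdrawal symptoms, mood, cognitive performance". The same sentence goes on to cigarette demand and to reward and satisfaction from a smoked cigarette.

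Baseline information appears elsewhere in the R21 plan, but not as adjustment in these models:

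- Baseline is a covariate in the cognitive ANOVAs: "cognitive measure scores (with baseline scores covaried".
- Screening BPRS is entered before Session 8 BPRS in a separate regression on latency.
- Some baseline scores are listed as mediators in their own right: "Hypothesized mediators will include baseline Calgary scale, cognitive performance and Contemplation Ladder scores".
- Gender and FTND are added to models as moderators: "We will examine whether gender and FTND score".

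**The concern.** Participants are randomised to varenicline or placebo, so the a path (drug to mediator) and the c path (drug to latency) are protected. Nobody is randomised to a Session 8 score, so the b path (mediator to latency) is an observational association within arms.

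Someone with strong urges before any drug is likely to have strong urges at Session 8, and may relapse sooner for reasons unrelated to the Session 8 urge itself. With only group and the Session 8 score in the equation, b picks up that stable difference between people. Multiplied by a genuine drug effect on urges, it yields a non-zero indirect effect even if the drop in urges did nothing to latency.

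What is at stake is the interpretation of Aim 2, whose whole content is mediation. The treatment comparisons in Aim 1 are not affected.

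**Working it through.** **Plan's own figure.** There is none to reproduce. The R21 sample-size section says the number was not chosen for Aim 2 and gives no power or error rate for mediation.

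**Inputs from the documents.** 48 randomised (24 per arm, taking equal allocation); design effect d = .40; 95% bootstrap interval for ab; significance level .05 (taken as two-sided).

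**Assumptions not in the documents.** r, the correlation of the pre-drug level with the Session 8 score: .5 to .7. g, the strength with which a higher pre-drug level predicts shorter latency: .3 to .5, with 0 as control. True effect of the Session 8 score on latency: zero. d, the reduction in the mediator on varenicline: .4 (design value) or .8 SD.

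**Large-sample bias.** Let T be the pre-drug level and G the group, with all within-arm variances 1:

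- Mediator: M = rT - dG + error
- Latency: Y = -gT + error, with no M term

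Regressing Y on G and M gives b = Cov(M, Y | G) / Var(M | G) = -rg, although the true value is 0. The range is -(.5 × .3) = -.15 to -(.7 × .5) = -.35. Since a = -d, ab tends to d × r × g:

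- d = .4: .4 × .15 = .06 to .4 × .35 = .14 SD of latency
- d = .8: .8 × .15 = .12 to .8 × .35 = .28 SD of latency

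N does not appear in these limits.

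**Simulation at n = 48** (600 trials per row, 600 percentile-bootstrap resamples each). The last two columns give the share of trials whose 95% interval for ab excludes zero.

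| d | r | g | limit of ab | group + Session 8 only | Session 1 added to both equations |
|---|---|---|---|---|---|
| .4 | .5 | 0 | 0 | 1.2% | 1.5% |
| .8 | .5 | 0 | 0 | 4.5% | 5.3% |
| .4 | .5 | .3 | .06 | 4.0% | 1.5% |
| .4 | .5 | .5 | .10 | 11.7% | 1.8% |
| .4 | .7 | .5 | .14 | 19.7% | 3.7% |
| .8 | .5 | .3 | .12 | 13.7% | 6.0% |
| .8 | .5 | .5 | .20 | 31.8% | 6.8% |
| .8 | .7 | .5 | .28 | 54.8% | 5.8% |

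The g = 0 rows show no inflation, so the excess comes from the confounder. At d = .4 the right benchmark is the 1.2% control rather than 5%, because the test of ab is conservative when a is weakly estimated: a single-time-point comparison at d = .40 with 24 per arm has only about 28% power.

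**Larger drug effects.** A similar simulation (1,500 trials per scenario) with effects of 0.6 to 1.0 SD gave 8.9% at the weak end (0.6, r = .5, g = .3) and 64.7% at the strong end (1.0, r = .7, g = .5). Adjusted rates were 3.7% and 7.1%.

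**Variations.**

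- Latency cut off at a ceiling (d = .8, r = .7, g = .5): 48% unadjusted, 5% adjusted.
- N = 200 (d = .4, r = .7, g = .5): 82% unadjusted, 7% adjusted. More participants make the false finding more likely.
- Session 1 score with reliability .7 (d = .8, r = .7, g = .5): the adjusted b tends to -rg(1 - .7)/(1 - .7r²) = -.105/.657 = -.16, so ab tends to .8 × .16 = .13. The simulated mean was .12, with 13% of intervals excluding zero, against 52% unadjusted.

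**The case against.** **The correlations are assumed.** This stands. No section relates a Session 1 score to latency. Session 1 precedes both medication and the abstinence period, whereas Session 8 follows three days of paid abstinence. A reader might infer that the b path is confounded as a matter of fact. The documents support only that it can be.

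**The high rates need effects beyond the design value.** This stands too. The plan designs for d = .40 and cites earlier effects of .32 to .44. At .40 the range is 4% to 20%, with the low end under the nominal 5%. The 65% requires an effect 1.0/.40 = 2.5 times the design value together with the strongest assumed correlations.

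**The bootstrap is conditional, and the mediation sample may be below 48.** The plan bootstraps only if ab is not normally distributed. A normal-theory test flags fewer trials: 0.3% to 7.0% at d = .40, and 2.5% to 47.6% for effects of 0.6 to 1.0 SD. Only those abstinent throughout complete Session 8. At an assumed n of 36 and d = .40 the bootstrap rate is 3.1% to 11.4%. Both points lower the rate of false findings; neither removes the bias in b.

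**A false indirect effect would rarely come with a significant drug effect on latency.** When varenicline truly has no effect on latency, both occur together in fewer than about 2% of trials, so a claim that varenicline delays relapse by reducing urges would usually lack a delay to explain. That defence fails when varenicline delays relapse by another route: with c = .8, d = .8, r = .7 and g = .5, both appear in about 45% of trials, and the delay would be credited to the wrong mechanism. The share is lower with weaker correlations. The plan does not require a significant c path before interpreting ab.

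**FTND already enters the models.** It enters as a dichotomised moderator, which is not the pre-drug level of the mediator.

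**Little depends on mediation.** The go/no-go rule rests on reduction of the targets, and Aim 2 did not set the sample size. This limits the consequence. Aim 2 is still one of only two R21 aims.

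**Conclusion.** The point holds for the models with Session 8 mediators. As specified, they can attribute to the mediator a difference between people that existed before the drug. The bias in ab is d × r × g: .06 to .14 SD of latency at the design effect and .12 to .28 SD at d = .8, at any sample size. The chance of a false indirect effect at n = 48 is about 4% to 20% at d = .40 and about 9% to 65% for effects of 0.6 to 1.0 SD. All of these figures rest on the assumed correlations and a true b of zero.

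Two stronger readings are not supported. One is that the trial's conclusions as a whole are at risk: Aim 1, the latency comparison, safety and the go/no-go decision do not use these models. The other is that baseline adjustment settles the matter: the near-zero bias after adjustment in the table arises because the only simulated confounder was measured without error. Measurement error at Session 1, unmeasured confounders and selection of those abstinent to Session 8 all remain.

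The change should be made because it is almost free, not because the R21 phase fails without it. The models that treat baseline scores as mediators are a separate matter and are not covered here.

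**What to change.** In the mediation paragraph of the Data Analysis Plan, R21 phase, before unblinding:

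1. For each Session 8 mediator (QSU, MNWS, CPT, CEQ Reward and Satisfaction, cognitive scores), add the Session 1 value of the same measure as a covariate in both the mediator equation and the latency equation.
2. Bootstrap ab from these adjusted equations.
3. State that b remains observational after adjustment, and name the remaining threats: error in the Session 1 measure, unmeasured confounders, and restriction to those abstinent to Session 8.

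FTND as a further covariate is optional; its benefit was not assessed here.

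The cost is a change of wording and one degree of freedom per equation (two with FTND). The Session 1 scores are already collected, so no new data, visits or participants are needed.
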